5.2 Study Primary Endpoints and Acceptance Criteria

The primary endpoints that will be evaluated in this clinical trial are RBC mass recovery, hemolysis and 24-hour in vivo red cell recovery. The endpoint-associated study acceptance criteria are listed below:

- A one-sided 95% lower confidence limit for the true proportion of packed RBC units with hemolysis at day 42 of < 1% is > 95%.
- The mean 24-hour, post-transfusion, in vivo red cell recovery of at least 75% with a standard deviation of $\leq 9\%$, and the lower limit of a one-sided 95% confidence interval for the population proportion of successes is $\geq 70\%$.
- Red Blood cell recovery $\geq 85\%$; with 95% confidence that at least 95% of units are $\geq 85\%$.

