6.2.8 Blood Product Sampling

Blood product containers will be thoroughly mixed prior to sampling to ensure a representative sample is obtained from a homogeneous blood product.

Study Protocol

Clinical Investigation to Evaluate the New Health Sciences Hemanext® Oxygen Reduction System for Leukoreduced Red Blood Cells with CP2D Anticoagulant and AS-3 Additive - Pivotal Trial

Protocol #: CLIN-0001

Date: 28 Nov 2017

Page 23 of 65

Thorough mixing of each whole blood unit prior to taking pre-filtration and post-filtration samples is of critical importance for the calculation of filtration red cell recovery.

All sample aliquots will be taken without damaging the integrity of the test system or blood unit. Evaluation samples from whole blood and RBC units will be taken via a sterile connection between a sterile transfer bag to the blood product container using an FDA approved sterile connection device and then transferring an aliquot to the transfer bag.

When sampling, care must be taken to ensure that air is not transferred to the blood component container from the sample transfer bag. If a red cell unit is removed from cold storage for sampling purposes it must be returned to cold storage (1-6°C) within 30 minutes of the time of removal.

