6.2.13 Endpoint Calculations

Study sites will perform real-time calculations (RBC mass) and batch testing (hemolysis) to determine whether study endpoints meet study criteria and specifications. Clinical sites will employ the formulas that follow to perform real-time calculations for the purpose of informing the study sponsor quickly when it appears that data relative to the study acceptance criteria appear to be out of the acceptable range. However, for the purpose of the database and resulting data, the raw values will be entered into the EDC database, and the reported values will be calculated separately.

Study Protocol

Clinical Investigation to Evaluate the New Health Sciences Hemanext® Oxygen Reduction System for Leukoreduced Red Blood Cells with CP2D Anticoagulant and AS-3 Additive - Pivotal Trial

Protocol #: CLIN-0001

Date: 28 Nov 2017

Page 25 of 65

24-hour in vivo RBC recovery and survival will occur per the procedures summarized in section 6.2.11, and clinical sites will use the raw data to perform their own 24-hour % RBC recovery and survival calculations. Only % Recovery and % Survival values will be entered into the study's EDC system. Formulas used and the means to perform calculations relative to RBC recovery are site-specific. Calculated values will be confirmed per data captured within the eCRF relative to confirmation of calculations during monitoring visits.

Upon performing calculations for recovery, should a calculated value fall outside of the protocol-specified endpoint criteria, then the sponsor will be notified as soon as possible and within 24 hours.

Study Protocol

Clinical Investigation to Evaluate the New Health Sciences Hemanext® Oxygen Reduction System for Leukoreduced Red Blood Cells with CP2D Anticoagulant and AS-3 Additive - Pivotal Trial

Protocol #: CLIN-0001

Date: 28 Nov 2017

Page 26 of 65

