6.2.14 RBC Filtration Recovery Calculation

RBC filtration recovery will be calculated via both a standard and the alternative method (using post filtration and pre-filtration weights). These calculations will be performed during the data analysis phase of the study based on hematocrit, volume and pre-/post filtration weights provided by sites. To better ensure accurate data, it is recommended that unit volumes be calculated from the weight of the full product. The results from both calculations will be reported.

RBC filtration recovery will be determined according to Figure 4. The acceptance criteria will be determined by the "standard equation" below.

Figure 4: RBC Recovery calculations (Standard and Alternate equations)**Standard equation:**

$$\text{RBC Recovery} = (\text{A} \times \text{Post-filtration unit volume}) / (\text{B} \times \text{Pre-filtration unit volume}) \times 100$$

Where: 'A' = Post-Hemanext HCT or RBC count

'B' = Pre-filtration HCT or RBC count

Unit volume (mL) = unit weight (g) / 1.056 (g/mL)

1.056 = relative density of whole blood

Alternate equation:

$$\text{RBC Recovery} = (\text{Post-filtration net unit weight}) / (\text{Pre-filtration net unit weight}) \times 100$$

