6.2.16 Study Activities

Study donors who are eligible for study participation will be assigned to either the in vitro portion only or in vivo and in vitro groups. Study donors will be enrolled until the intended total of evaluable units has been collected. Note that cited days reference the number of days post collection.

See Tables 5-7 for summary of analyses and data collection.

Study Protocol

Clinical Investigation to Evaluate the New Health Sciences Hemanext® Oxygen Reduction System for Leukoreduced Red Blood Cells with CP2D Anticoagulant and AS-3 Additive - Pivotal Trial

Protocol #: CLIN-0001

Date: 28 Nov 2017

Page 27 of 65

- a) After signing the respective consent documentation, collect and record data relative to inclusion/exclusion criteria, demographics, concomitant medications and medical history.
- b) Collect and record the collection set's identification numbers.
- c) Collect a whole blood unit using the product per the IFU. Draw a sample of the study donor's native whole blood from the diversion bag and place aliquots in tubes for the indicated analyses.
- d) As soon as reasonably possible after collection, place anticoagulated whole blood units into room temperature storage until filtration.
- e) Immediately prior to filtration, weigh, sample and re-weigh each whole blood unit.
- f) Initiate room temperature filtration for each unit (5-7 hours post-collection). Record filtration-associated data.
- g) Weigh, sample and then re-weigh filtered whole blood units.
- h) As soon as practical following the completion of filtration, the LRWB units will be centrifuged and processed at room temperature to separate the unit into PRBCs and PPP. Record centrifugation-associated data.
- i) AS-3 will be mixed with the PRBCs as soon as practical following separation from the plasma.
- j) Following processing, the additive RBC unit will be weighed.
- k) Plasma will be discarded.
- l) The unit will be sampled and weighed.
- m) If the unit is in the CP arm then at this point it will be placed in refrigerated storage (1-6°C; within 8 hours of donation).
- n) If the unit is in the IP arm then the AS-3 LR-RBC unit will be transferred to the Hemanext ORB (within 8 hours of donation) at which point the unit will be weighed to ensure that the volume of the unit is less than 350 mL.
- o) The ORB will be placed on a Helmer Platelet Shaker for 3 hours + 15 minutes.

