6.2.16.6 Post-filtration

The unit will be weighed, sampled, and re-weighed.

- Sampling time and temperature
- Filtered WB Unit Pre-sample Gross Weight
- Filtered WB Unit Post-sample Gross Weight
- CBC
 - WBC Count
 - RBC Count

Study Protocol

Clinical Investigation to Evaluate the New Health Sciences Hemanext® Oxygen Reduction System for Leukoreduced Red Blood Cells with CP2D Anticoagulant and AS-3 Additive - Pivotal Trial

Protocol #: **CLIN-0001**

Date: 28 Nov 2017

Page 36 of 65

- MCV
 - MCH
 - MCHC
 - RDW
 - PLT Count
 - Total Hemoglobin
 - Hematocrit
- Supernatant Hgb
- Spun Hematocrit
- rWBC Count

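### The equation that decides the RBC recovery endpoint multiplies a post-Hemanext concentration by a post-filtration volume, which overstates recovery and leaves control units without a value

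*Combined protocol and SAP*

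**What the plan says.** Section 5.2 lists the primary endpoints as "RBC mass recovery, hemolysis and 24-hour in vivo red cell recovery" and requires RBC recovery of at least 85%, with 95% confidence that at least 95% of units reach it. Section 5.3.1 turns this into at least 92 passes in 93 units, with the study discontinued at two failures.

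Section 6.2.14 is headed as filtration recovery and makes the standard equation of Figure 4 decisive. That equation is A times "Post-filtration unit volume", divided by B times the pre-filtration unit volume, times 100. A is defined as "Post-Hemanext HCT or RBC count" and B as the corresponding pre-filtration value.

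On use of the formula, section 6.2.13 says: "Clinical sites will employ the formulas that follow to perform real-time calculations". On sampling, section 6.2.8 says that thorough mixing "prior to taking pre-filtration and post-filtration samples is of critical importance for the calculation of filtration red cell recovery".

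The two stages in the numerator are defined elsewhere:

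- **Post-filtration.** Section 6.2.16 step g: "Weigh, sample and then re-weigh filtered whole blood units". Section 6.2.16.6 records "Filtered WB Unit Pre-sample Gross Weight". Tables 6 and 7 label the product LR WB. This comes before centrifugation, plasma removal and AS-3.
- **Post-Hemanext.** Steps h to p of section 6.2.16, section 6.2.16.10 and a separate column of Table 6 place this after plasma removal, AS-3 and the oxygen reduction bag. It exists for investigational units only.

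**The concern.** Red cell mass is concentration times volume in one container at one time. Figure 4 takes the concentration from the packed AS-3 unit and the volume from the filtered whole blood it was made from. The packed unit is smaller and has the higher hematocrit, so the product exceeds the red cell mass at either stage.

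This equation decides one of three primary endpoints. If it is applied as printed, the 92-of-93 rule and the two-failure discontinuation rule are both judged against a threshold lower than 85%, and the sites' real-time alerts are muted in the same way.

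Two related gaps make the repair ambiguous. Section 5.2 speaks of mass recovery, while sections 6.2.8 and 6.2.14 speak of filtration recovery, so either A or the volume could be the mislabelled term. And Table 7 has no post-Hemanext column, so A does not exist for control units, although section 5.3.1 words its failure rule to cover any study arm.

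**Working it through.** **1. The plan's own decision rule.** With X ~ Bin(93, 0.95), P(X ≥ 92) = 0.04998. With 92 units and one failure allowed it is 0.0521. So 93 is the smallest number that supports one failure at 95%/95%. The rule is sound; the problem is the quantity fed into it.

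**2. What the printed equation computes.** Let Vpf be the post-filtration volume, VH the post-Hemanext volume and Vpre the pre-filtration volume.

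Printed result = (A × Vpf)/(B × Vpre) = [(A × VH)/(B × Vpre)] × (Vpf/VH)

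The bracket is true whole-process recovery, so the overstatement factor is Vpf/VH.

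**3. Inputs.**

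- VH: step n of section 6.2.16 requires the unit entering the oxygen reduction bag to be "weighed to ensure that the volume of the unit is less than 350 mL". Section 6.2.16.9 gives a net weight below 370 g, and 370/1.056 = 350.4 mL. I use 350 mL. Later steps add no volume, and a smaller VH makes the factor larger.
- Vpf: not stated, so assumed at 400 to 550 mL. As a partial anchor, sections 5.3.5.1 and 6.2.4 give a collection of 450 to 550 mL that includes 20 to 40 mL of samples. That leaves 450 − 40 = 410 to 550 − 20 = 530 mL of blood, or factors of 410/350 = 1.17 to 530/350 = 1.51, if anticoagulant, filter hold-up and pre-filtration sampling cancel (an assumption).

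**4. Size with VH = 350 mL.**

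| Vpf (mL, assumed) | Factor | True recovery that scores 85% | Score of a true 80% |
|---|---|---|---|
| 400 | 1.143 | 74.4% | 91.4% |
| 450 | 1.286 | 66.1% | 102.9% |
| 500 | 1.429 | 59.5% | 114.3% |
| 550 | 1.571 | 54.1% | 125.7% |

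With VH = 300 mL (assumed) the factors are 1.33 to 1.83. The factor falls to 1 only in a corner case: 410 mL in the bag, no anticoagulant counted, 60 mL lost at filtration and a full 350 mL final unit, (410 − 60)/350 = 1.00.

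**5. Effect on the decision (illustration).** Assume true whole-process recovery is normal with mean 80%, a product that should fail. With p = P(recovery ≥ 85/factor), the chance of at least 92 of 93 passes is:

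| Factor | SD 3 | SD 4 | SD 5 |
|---|---|---|---|
| 1.00 (stages matched) | 0.000 | 0.000 | 0.000 |
| 1.143 | 0.222 | 0.004 | 0.000 |
| 1.286 | 1.000 | 1.000 | 0.973 |
| 1.429 and 1.571 | 1.000 | 1.000 | 1.000 |

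**6. One worked unit (all values assumed).** Pre-filtration 560 mL at Hct 38%, post-filtration 515 mL at 38%, post-Hemanext 330 mL at 56%.

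- Filtration recovery: (515 × 38)/(560 × 38) = 92.0%.
- Whole-process recovery: (330 × 56)/(560 × 38) = 86.8%.
- Figure 4 as printed: (515 × 56)/(560 × 38) = 135.5%, which is impossible as a recovery.

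If the intended endpoint is filtration recovery, the factor is instead the hematocrit ratio, 56/38 = 1.47, against 515/330 = 1.56 on the whole-process reading. Both are well above 1.

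**The case against.** The strongest reply is that this is a labelling slip that would expose itself. At factors of 1.29 and above, where a poor product would pass almost surely, the average unit with a true 80% scores above 100%. At 1.14, where 80% reads a plausible 91%, the pass probability is at most 0.22. So the range in which the error is both decisive and unnoticed is narrow for that product. The raw values are kept, reported values are calculated separately from the sites' alerts, and the alternate equation is also reported. This makes the error correctable, but it does not repair the definition. Section 6.2.14 assigns the same printed equation to the analysis phase, the alternate equation is a weight ratio with no red cell concentration and does not decide acceptance, and correcting a primary endpoint formula after seeing its values is avoidable.

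Several narrower points stand:

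- The thresholds of 74% to 54% refer to whole-process recovery. On the filtration reading the factor is the hematocrit ratio; the direction is unchanged.
- If the post-filtration volume was meant loosely as the final unit's volume, the overstatement disappears. Nothing in the text says so.
- Section 5.3.1 also speaks of test units, so the pass criterion may be meant for investigational units only. The any-arm wording of the failure rule, and the between-arm comparisons in section 5.4, still need a control formula.
- Section 6.2.14 says the calculation is based on hematocrit, which partly answers the open choice in A. The definition of A still offers either measure.
- The mean of 80% and SD of 3 to 5 points are assumptions, and the low-end figure is fragile: rounding the factor from 1.143 to 1.14 moves 0.22 to 0.16.

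**Conclusion.** The concern holds. The decisive equation combines two stages that the protocol itself keeps apart, and no other section repairs it. The mismatch is certain, and the upward direction follows from the plan's own volumes on either reading of the endpoint, apart from the corner case shown. The size is less certain because filtered, anticoagulant and hold-up volumes are not given. Over the assumed 400 to 550 mL with a 350 mL final unit, the 85% threshold becomes an effective 74% to 54% of whole-process recovery. At the low end the criterion can still be failed; from a factor of about 1.3 it is very hard to fail. The equation has no defined value for control units. This should be corrected before the endpoint is analysed.

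**What to change.** 1. State whether the primary endpoint is filtration recovery or whole-process RBC mass recovery, and bring sections 5.2, 6.2.8 and 6.2.14 into line.
2. Take concentration and volume from the same container and time:
   - *Filtration recovery, both arms:* (post-filtration Hct × post-filtration volume) / (pre-filtration Hct × pre-filtration volume after sampling) × 100.
   - *Whole-process recovery:* numerator is post-Hemanext Hct × post-Hemanext volume for test units, and baseline AS-3 red cell Hct × its volume for control units. Both go over the same denominator, corrected for volume sampled out in between using the recorded pre- and post-sample weights. State the density to be used for the AS-3 red cell unit, since 1.056 is labelled as that of whole blood.
3. Name one measure, Hct or RBC count, in advance.
4. Say in section 5.3.1 whether the criterion applies to control units.
5. Report the other recovery as supportive, and query any unit with a calculated recovery above 100%.

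The cost is one endpoint definition and one corrected equation in the protocol, plus a check of the separate SAP and the site worksheets for the same wording. Sections 6.2.16.4, 6.2.16.6, 6.2.16.8 and 6.2.16.10 already collect the weights and hematocrits, so no new sampling is needed.

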5.3 Donor/Data Criteria**5.3.1 Sample Size**

The sample sizes described within the protocol were selected to demonstrate meeting study primary endpoints that conform to the FDA's 95-95 rule (95% confidence and 95% reliability). For successful endpoint outcomes, the study requires meeting the acceptance criteria in 92 of 93 test units per test condition. Therefore, 93 evaluable study donors will complete the study. In the event of two (2) donors/units with unmet acceptance criterion occurring out of ninety-three (93) evaluable procedures (i.e., within one or more study arm(s) for one or more acceptance criteria/primary endpoints), the study will be discontinued.

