5.4 Statistical Analysis Plan

The data from this study will be analyzed to determine whether the primary endpoints and study acceptance criteria (as recommended by FDA and as listed in section 5.2) were met.

In order to assure that 95% confidence in 95% reliability of the of the lower confidence level of the units meet the acceptance criteria for the primary endpoints, the sample size shall be:

- Ninety-three (93) evaluable procedures in which no more than one (1) failure occurs against the acceptance criteria for the primary endpoints.

Secondary analyses, such as differences in populations by site and comparisons between arms, will be described in more detail within the statistical analysis plan. This formal SAP will be developed in conjunction but separately from this protocol, and filed within the trial master file.

The following, at a minimum, will be presented using descriptive statistics:

- **Donor Disposition:** All data on all study donors enrolled in trial including data identified as evaluable and non-evaluable donations will be presented.
- **Demographics:** Age, gender, weight, height, ethnicity and race will be provided for all study donors enrolled in the trial for both evaluable and non-evaluable donations. A comparison to census data will be performed in the final report.
- **Collection procedure-related data:** Collection duration and ambient temperatures will be provided for both evaluable and non-evaluable donations.

Study Protocol

Clinical Investigation to Evaluate the New Health Sciences Hemanext® Oxygen Reduction System for Leukoreduced Red Blood Cells with CP2D Anticoagulant and AS-3 Additive - Pivotal Trial

Protocol #: CLIN-0001

Date: 28 Nov 2017

Page 20 of 65

- **Filtration & processing procedure-related data:** Temperature, head height, filtration time, filter time, filter weight, and final collection volumes will be provided for evaluable and non-evaluable donations.
- **Laboratory data:** Laboratory data will be provided for evaluable and non-evaluable donations (if applicable). Other than the endpoints detailed in the acceptance criteria, the laboratory data will be presented for information only.
- **Adverse events:** Expected, unexpected and serious adverse events will be reported for all enrolled study donors.

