6.2.15 Hemolysis Calculation

Supernatant hemoglobin will be tested and % hemolysis calculated.

% Hemolysis will be determined according to the equation in Figure 5 and using Spun Hematocrit only.

Figure 5: Hemolysis calculation

$$\% \text{ Hemolysis} = \frac{(\text{Supernatant Hgb (mg/dL)} \times 0.001) \times ((1 - (\text{Hct} \times 0.01)) \times 100)}{\text{Total Hgb (g/dL)}}$$

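### The equation that decides the RBC recovery endpoint allows hematocrit or RBC count, with no rule for choosing and no requirement that numerator and denominator match

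*Combined protocol and SAP*

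**What the plan says.** Section 5.2 lists RBC mass recovery as a primary endpoint. Its criterion is "Red Blood cell recovery" of at least 85%, "with 95% confidence that at least 95% of units are" 85% or more. Section 5.3.1 turns this into meeting the criterion in "92 of 93 test units per test condition"; with two failures, in one or more arms, "the study will be discontinued". Section 5.4 repeats the rule: "Ninety-three (93) evaluable procedures in which no more than one (1) failure occurs against the acceptance criteria for the primary endpoints".

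Section 6.2.14 gives a standard and an alternate equation and says the standard one settles acceptance. In Figure 4 that equation is A times the post-filtration unit volume, divided by B times the pre-filtration unit volume. A is "Post-Hemanext HCT or RBC count" and B is "Pre-filtration HCT or RBC count". The text introducing the calculation names hematocrit, volume and weights as the site inputs; it does not mention RBC count and does not say which hematocrit is meant.

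Analyzer hematocrit, spun hematocrit, RBC count and MCV are all recorded at pre-filtration (6.2.16.4), post-filtration (6.2.16.6) and post-Hemanext (6.2.16.10). For hemolysis, section 6.2.15 does fix the measure: "using Spun Hematocrit only". Recovery has no such statement.

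**The concern.** A pass/fail primary endpoint needs one value per unit. Figure 4 admits three: by RBC count, by analyzer hematocrit and by spun hematocrit. It does not require A and B to be the same kind. Putting a count in one place and a hematocrit in the other would give an obviously wrong number. Putting spun hematocrit in one place and analyzer hematocrit in the other would not be noticed, because both are percentages.

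The versions answer slightly different questions. A count-based ratio measures cells recovered. A hematocrit-based ratio measures packed cell volume recovered, and so also reflects any change in cell size between the two samples.

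The acceptance rule sits exactly at its limit, so one unit changing status can decide the endpoint. Under section 6.2.13 the sites calculate RBC mass recovery in real time to alert the sponsor, and the reported values are calculated separately from the raw data. The two could use different measures while both follow Figure 4.

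**Working it through.** **1. The plan's own figure.** Require P(at most 1 failure in n | failure rate 5%) to be no more than 0.05, by the exact binomial.
- n = 92: 0.0521. n = 93: 0.04998. The minimum is 93, as the plan states.
- Exact one-sided 95% lower limits: 92/93 gives 95.0% and 91/93 gives 93.4%. A single extra failure turns a pass into a fail.

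**2. How the two measures relate.** Analyzer hematocrit = RBC count × MCV, up to units. With the same volumes in both versions,

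recovery by hematocrit = recovery by count × (MCV post / MCV pre).

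This is exact for analyzer hematocrit; spun hematocrit can differ further.

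**3. Size for one unit.** The documents give no MCV change. Assume a range of ±2% to ±5%, for a unit at 85.0% by count:

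| Assumed MCV change | Reads by hematocrit | Count recoveries for which the verdicts differ |
|---|---|---|
| −5% | 85 × 0.95 = 80.8% | 85.0% to 85/0.95 = 89.5%: pass by count, fail by hematocrit |
| −2% | 85 × 0.98 = 83.3% | 85.0% to 85/0.98 = 86.7%: pass by count, fail by hematocrit |
| +2% | 85 × 1.02 = 86.7% | 85/1.02 = 83.3% to 85.0%: fail by count, pass by hematocrit |
| +5% | 85 × 1.05 = 89.3% | 85/1.05 = 81.0% to 85.0%: fail by count, pass by hematocrit |

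**4. Size for the endpoint.** The documents give no recovery distribution. Assume count recovery is normal with mean m and SD 2.5%, and let k be the MCV ratio. The failure probability per unit is Φ((85 − m·k)/(2.5·k)), and the endpoint is met with at most 1 failure in 93.

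| Assumed mean | By count (k = 1) | By hematocrit, k = 0.98 | By hematocrit, k = 0.97 |
|---|---|---|---|
| 92% | 0.98 | 0.51 | 0.11 |
| 94% | 1.00 | 0.99 | 0.91 |

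For example, with m = 92 and k = 0.98, (85 − 90.16)/2.45 = −2.11. That gives a failure probability of 0.0176 and a chance of 0.51 of meeting the rule. The effect depends heavily on how far typical recovery lies above 85%.

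**5. The condition behind steps 2 to 4.** Concentration and volume must come from the same stage. As printed they do not. A is post-Hemanext, which is red cells in AS-3, but it multiplies the post-filtration volume, which in the step order of section 6.2.16 is whole blood before plasma removal. Taken literally, with assumed hematocrits of 36% to 40% before and 50% to 60% after, and a volume ratio of 0.85 to 0.95:
- lowest: 50 × 0.85 / 36 = 118%
- highest: 60 × 0.95 / 40 = 142.5%

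On those inputs no unit comes near 85% by either measure. The printed A also does not exist for control units: section 6.2.16.10 is for the investigational product only, and Table 7 has no post-Hemanext column.

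**The case against.** Several points on the other side stand.

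- The text of section 6.2.14 names hematocrit as the input, so the two measures are not equally open. This narrows the gap but does not close it: Figure 4 still offers the count, and the kind of hematocrit stays unstated.
- A reader might infer that AS-3 and gas removal shift MCV and so bias the hematocrit version. The documents do not support that as a finding. They report no MCV change, and the section title, together with the emphasis in section 6.2.8 on mixing before pre- and post-filtration sampling, suggests that A may have been meant as the post-filtration sample. Both samples would then be CP2D whole blood on either side of the filter, and the reason to expect an MCV shift largely falls away.
- A reader might infer that the measure can be picked once results are known. That cannot be asserted. Section 5.4 announces a separate formal SAP, whose text is not in the document under review and which may fix the choice.
- Sites and sponsor using different measures would affect an alert, not the reported endpoint, because reported values are recalculated from raw data.
- If recoveries lie well above 85%, the choice may not matter, as the 94% row shows.

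None of this supplies the missing rule, and sites apply the protocol's formula whatever the separate SAP says.

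**Conclusion.** The point holds as a gap in specification. The equation that decides a primary endpoint leaves its concentration measure open, does not require A and B to match, and conflicts with the sentence that introduces it. Under an assumed 2% MCV change the difference is 1.7 percentage points for a unit at 85.0%, so a verdict could change only for units close to the threshold. How many such units there will be is unknown, and the shift is likely to be smaller if A is meant to be the post-filtration whole-blood sample. The documents do not show that the endpoint result would change, or in which direction. It is still worth correcting before data are analyzed, because the rule of at most one failure in 93 leaves no room for a disputed unit.

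**What to change.** In Figure 4, and in the section 6.2.14 sentence that names hematocrit, state that A and B are both the analyzer RBC count, for the sites' real-time check and for the reported value. The count does not depend on cell volume and is already collected at each stage. Report the spun-hematocrit version, with spun values in both places, as a sensitivity result. Carry the same definition into the separate SAP.

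In the same edit, reconcile the stages: take the concentration and the volume in each term from the same sample point, and define a numerator sample that exists for control units.

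The cost is two edits in section 6.2.14 and the matching SAP text. No new data are needed and N stays at 93. The downside is that RBC count has its own analyzer imprecision, against which the hematocrit sensitivity result gives a check.

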6.2.16.9 Hemanext Processing (IP only)

If the unit is in the IP arm it will be transferred to the ORB and will undergo the Hemanext process per the Hemanext IFU.

Hemanext Processing data collection are as follows:

- Lot #
- ORB Gross Weight (net weight should be < 370g)
- Time ORB placed on agitator
- Time ORB removed from agitator
- IFU confirmation

For the purpose of this study:

- For the procedural IFU confirmation, a response indicative of a deviation from the IFU will result in a prompt to record a protocol deviation in a separate Comments eCRF or other log.

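### Figure 4 supplies only a whole-blood density; if the RBC recovery numerator is the AS-3 red cell unit, reported recovery is off by the ratio of the two products' densities

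*Combined protocol and SAP*

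**What the plan says.** Section 6.2.14 (Figure 4) defines RBC recovery as concentration times unit volume after processing, over concentration times unit volume before filtration. On which of its two equations decides acceptance it says: "The acceptance criteria will be determined by the 'standard equation' below".

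- One conversion serves all volumes: "Unit volume (mL) = unit weight (g) / 1.056 (g/mL"), with the label "1.056 = relative density of whole blood".
- The denominator concentration is "B' = Pre-filtration HCT or RBC count", measured on whole blood plus CP2D.
- The numerator concentration is "A' = Post-Hemanext HCT or RBC count", measured on the red cell unit after plasma removal, AS-3 addition and oxygen reduction.
- The numerator volume is called the post-filtration unit volume. Elsewhere that stage is leukoreduced whole blood: step g of 6.2.16 reads "Weigh, sample and then re-weigh filtered whole blood units", and Table 6 and section 6.2.16.6 agree. Section 6.2.8 links filtration recovery to samples of the same kind: "Thorough mixing of each whole blood unit prior to taking pre-filtration and post-filtration samples is of critical importance".

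Section 5.2 requires recovery of at least 85% per unit, with 95% confidence that at least 95% of units reach it. Section 5.3.1 turns this into 92 of 93 units and discontinues the study at two failures.

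**The concern.** Whole blood plus CP2D and an AS-3 red cell unit are different mixtures. Plasma has been removed, additive put in, and the hematocrit raised. The protocol separates red cells from plasma by hard-spin centrifugation, which works because red cells are denser, so equal density of the two products cannot be taken for granted. A single divisor assumes exactly that.

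The criterion is a fixed line applied unit by unit, with one failure allowed. An error that comes from the conversion formula does not average out over 93 units. If recoveries lie close to 85%, a shift of less than one point could alter the real confidence behind the 95/95 statement.

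**Working it through.** **1. The plan's own figure.** With at most one failure and true reliability 95%, the chance of passing is 0.95^n + n × 0.05 × 0.95^(n−1). This is 0.0521 at n = 92 and 0.04998 at n = 93. So 93 is the smallest adequate number, as the plan states, and nothing below changes it.

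**2. The constant cancels.** Write A and B for the two concentrations and W for weight.

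Reported = (A × Wpost/1.056) / (B × Wpre/1.056) = (A × Wpost) / (B × Wpre).

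Illustration with A = 57, B = 38, Wpost = 340 g, Wpre = 560 g: the result is 91.07% whether the divisor is 1.0, 1.056 or 1.1. Because weight = true volume × true density,

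reported = true recovery × (density of post unit / density of pre unit).

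The value 1.056 does not matter; only the ratio of the true densities does.

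**3. Which unit is the numerator?**

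- *Volume from filtered whole blood, A from the post-Hemanext unit (Figure 4 taken literally).* With assumed hematocrit 38% before and 50–60% after, and 90–95% of volume kept, the result runs from 50/38 × 0.90 = 118% to 60/38 × 0.95 = 150%. These cannot be recoveries.
- *Both from the post-Hemanext AS-3 unit (A kept as written).* Section 6.2.16.10 collects the weights. The density ratio of step 2 applies.
- *Both from filtered whole blood (A moved).* Both products are whole blood, so no AS-3 density enters.

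**4. Size under the second reading.** The documents give no AS-3 unit density. The ORB loading limits are a volume below 350 mL (6.2.16, step n) and "net weight should be < 370g" (6.2.16.9). Their quotient is 370/350 = 1.0571, a ratio to 1.056 of 1.001. But 350 × 1.056 = 369.6, so the pair looks like the whole-blood constant reused and rounded, not an independent measurement.

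Assumed ranges instead: red cells 1.08–1.10; plasma 1.02–1.03; AS-3 1.00–1.02; CP2D 1.01–1.03; hematocrit 33–43% before and 50–65% after; suspending fluid 82% plasma and 18% CP2D before, 25% plasma and 75% AS-3 after.

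At the midpoints:
- Before: 0.38 × 1.09 + 0.62 × (0.82 × 1.025 + 0.18 × 1.02) = 1.0491.
- After: 0.575 × 1.09 + 0.425 × (0.25 × 1.025 + 0.75 × 1.01) = 1.0576.
- Ratio: 1.008.

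Over the full grid the ratio runs from 0.993 to 1.026, median 1.008. A reported 85.0% is then a true 85.6% at 0.993, 84.3% at 1.008 and 82.9% at the upper end.

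**5. Effect on the decision.** Assume normal recoveries, SD 1.5, 2 or 3 points, and mean = 85 + 1.645 × SD, so that true reliability is exactly 95%. A unit fails as reported with probability p = Φ((85/ratio − mean)/SD), and P(pass) is the binomial probability of at most one failure in 93.

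| Ratio | SD 1.5 | SD 2 | SD 3 |
|---|---|---|---|
| 1.000 | 5.0% | 5.0% | 5.0% |
| 1.004 | 21.7% | 16.1% | 11.5% |
| 1.008 | 50% | 35% | 22% |
| 0.993 | <0.1% | 0.2% | 0.6% |

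Away from the boundary the effect fades. With an assumed mean of 92 and SD 2, P(pass) is at least 0.998 at every ratio from 0.993 to 1.026. With mean 94 and SD 3 it is at least 0.976.

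**The case against.** The strongest reply is that Figure 4 never says the AS-3 unit's weight is converted. The section is about filtration recovery, its volume is labelled post-filtration, and the protocol consistently uses that term for filtered whole blood. On that view 1.056 is applied only to whole blood, and the real defect is the stage attached to A. This stands as far as it goes: conversion of the AS-3 weight is an inference from the definition of A. It does not dispose of the point, because the formula as printed cannot yield a recovery. One of the two repairs, matching the volume to A, brings the density ratio in. Correcting the volume label alone would leave it there.

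It is also fair that the documents do not show the densities to differ. The 350 mL and 370 g limits cannot settle this either way, since they appear to come from the same constant. The size rests wholly on assumed inputs and the range straddles 1. About nine in ten grid combinations exceed 1 (89% or 93%, depending on grid spacing), but that counts grid points and is not a probability.

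Finally, section 6.2.13 has raw values entered and reported values calculated separately, so the correction can be computed from stored data. That lowers the cost of the repair. It does not remove the need to fix the deciding version before analysis.

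**Conclusion.** The point holds conditionally. Figure 4 provides one whole-blood density and mixes two stages in its numerator. If the numerator is the AS-3 red cell unit, reported recovery is true recovery times a density ratio of about 0.993 to 1.026 (median about 1.008, or 85 × 0.008 ≈ 0.7 points at 85%), given the assumed densities, hematocrits and fluid splits. The likely direction favours the device.

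Three stronger conclusions might be drawn, and the documents support none of them:

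- That the primary endpoint is definitely misstated. This depends on which product supplies the numerator, and Figure 4 leaves that open.
- That all 93 units move the same way by the same amount. The ratio depends on each unit's hematocrit before and after, and the assumed range includes both signs.
- That the trial would pass or fail wrongly. The pass probabilities of 11–50% (and under 1% at 0.993) apply only when true reliability sits exactly at 95%. The documents give no mean or SD for recovery, and with recoveries well above 85% the decision is unaffected.

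The sample size of 93 stands.

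**What to change.** In section 6.2.14:

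1. State which product's weight and hematocrit (or RBC count) form the numerator, both taken at the same stage, for each arm. The control arm needs its own definition, because Table 7 has no post-Hemanext sample.
2. If the numerator is the AS-3 unit, divide each weight by the density of the product weighed. Use either one prespecified value for whole blood plus CP2D and one for AS-3 red cells, or a density computed from the spun hematocrit already measured pre-filtration and post-Hemanext. Let this version decide acceptance, and report the single-1.056 result as a sensitivity analysis.
3. If A is instead moved to the filtered whole blood stage, say so. No AS-3 density correction is then needed, but the endpoint measures filtration alone.

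The cost is protocol and SAP wording plus one or two constants, with no new samples or visits. The density values must be sourced and fixed before analysis, and reported recovery may come out slightly less favourable.
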